4.5.5.2 Ipilimumab Dose Discontinuation (Arm A)

Ipilimumab should be permanently discontinued if any of the following criteria are met:

- Any Grade \geq 2 drug-related uveitis or eye pain or blurred vision that does not respond to topical therapy and does not improve to Grade 1 severity within 2 weeks OR requires systemic treatment;
- Any Grade \geq 3 bronchospasm or other hypersensitivity reaction;
- Any other Grade 3 non-skin, drug-related adverse event with the following exceptions for laboratory abnormalities, Grade 3 nausea and vomiting, Grade 3 neutropenia and thrombocytopenia, and symptomatic endocrinopathies which resolved (with or without hormone substitution);

- Any drug-related liver function test (LFT) abnormality that meets the following criteria require discontinuation:
 - AST or ALT > 8x ULN
 - Total bilirubin > 5 x ULN
 - Concurrent AST or ALT > 3 x ULN and total bilirubin > 2 x ULN
- Any Grade 4 drug-related adverse event or laboratory abnormality, except for the following events, which do not require discontinuation:
 - Grade 4 neutropenia ≤ 7 days
 - Grade 4 lymphopenia or leukopenia
 - Isolated Grade 4 amylase or lipase abnormalities which are not associated with symptoms or clinical manifestations of pancreatitis.
 - Isolated Grade 4 electrolyte imbalances/abnormalities that are not associated with clinical sequelae and are corrected with supplementation/appropriate management within 72 hours of their onset
- Any treatment delay resulting in no ipilimumab dosing for > 12 weeks with the following exceptions: Dosing delays to manage drug-related adverse events, such as prolonged steroid tapers, are allowed. Prior to re-initiating treatment in a participant with a dosing delay lasting > 12 weeks, the BMS medical monitor must be consulted. Tumor assessments should continue as per protocol even if dosing is delayed.
- Dosing delays resulting in no ipilimumab dosing for > 12 weeks that occur for non-drug-related reasons may be allowed if approved by the BMS medical monitor. Prior to re-initiating treatment in a participant with a dosing delay lasting > 12 weeks, the BMS medical monitor must be consulted. Tumor assessments should continue as per protocol even if dosing is delayed.
- Any adverse event, laboratory abnormality, or intercurrent illness which, in the judgment of the Investigator, presents a substantial clinical risk to the participant with continued ipilimumab dosing

The assessment for discontinuation of ipilimumab should be made separately from the assessment made for discontinuation of nivolumab. Although there is overlap among the discontinuation criteria, if discontinuation criteria are met for ipilimumab but not for nivolumab, treatment with nivolumab may continue if ipilimumab is discontinued.

If a participant meets criteria for discontinuation and investigator is unable to determine whether the event is related to both or one study drug, the participant should discontinue both nivolumab and ipilimumab and be taken off the treatment phase of the study.

4.5.5.3 EXTREME Regimen Dose Discontinuation (Arm B)

Treatment should be permanently discontinued for the following:

- Any drug-related Grade 4 toxicity including laboratory abnormalities the subject will be discontinued from the relevant study drug, with the following exceptions:
 - Isolated Grade 4 electrolyte abnormalities not associated with clinical sequelae and are adequately managed and corrected within 72 hours of onset.
 - Grade 4 neutropenia or lymphopenia ≤ 7 days
- Any Grade 3 non-skin, drug-related adverse event lasting > 7 days, with the following exceptions:
 - Grade 3 drug-related laboratory abnormalities do not require treatment discontinuation, except for the following scenarios:
 - ◆ Grade 3 drug-related thrombocytopenia associated with bleeding
 - ◆ Any of the following drug-related liver function test (LFT) abnormalities:
 - AST or ALT > 8 x ULN
 - Total bilirubin > 5 x ULN
 - Concurrent AST or ALT > 3 x ULN and total bilirubin > 2 x ULN
 - ◆ Calculated creatinine decreases to < 60 mL/min based on Cockcroft Gault formula on participants receiving cisplatin. Switch to carboplatin is allowed at the discretion of investigator for the remaining cycles. See re-treatment criteria [section 4.5.4.3](#)
 - Any dosing delay lasting > 6 weeks, with the following exceptions:
 - If local standards allow dosing delays > 6 weeks for drug-related AEs, contact the BMS Medical Monitor prior to re-initiating treatment.
 - Dosing delays > 6 weeks that occur for non-drug-related reasons may be allowed if approved by the BMS Medical Monitor. Prior to reinitiating treatment in a participant with a dosing delay lasting > 6 weeks, the BMS Medical Monitor must be consulted. Tumor assessments should continue as per protocol even if dosing is delayed.
- Any adverse event, laboratory abnormality, or intercurrent illness which, in the judgment of the Investigator, presents a substantial clinical risk to the participant with continued treatment.

Participants who discontinue one of the study drugs in Arm B may, at the investigators discretion, continue administration of the other study drugs. For example, if 5-FU is discontinued, cetuximab and platinum agent may be continued at the intended dose and schedule.

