4.5.3.2 EXTREME Regimen

This section includes information on dose modifications for cetuximab, cisplatin or carboplatin and 5-FU treatment related toxicities.

A maximum of 2 dose reductions per study drug are permitted; if additional reductions are required, that particular study drug must be discontinued. Once a dose has been decreased, it should remain reduced for all subsequent dosing unless dose is further reduced. No dose escalations will be allowed. If one of the study drugs is delayed due to drug related toxicities during a treatment cycle, the other study drugs in the regimen may be administered at the discretion of the investigator; when dosing is resumed, dose reduction should only be applied to the study drug that was withheld.

Participants who discontinue one of the study drugs may, at the investigators discretion continue administration of the other study drugs in the regimen.

For Cetuximab: Dose modifications are permitted, as follows:

Infusion Reactions:

- Reduce the infusion rate by 50% for NCI CTC Grade 1 or 2 and non-serious NCI CTC Grade 3 infusion reactions.
- Immediately and permanently discontinue cetuximab for serious infusion reactions, requiring medical intervention and/or hospitalization.
- See [Section 4.5.8.2](#) for treatment of Cetuximab Infusion Reactions.

Dermatologic Toxicity: Table 4.5.3.2-1 contains the recommended dose modifications for severe (CTCAE v4 Grade 3 or 4) acneiform rash.

Table 4.5.3.2-1: Cetuximab Dose Modification Guidelines for Rash			
Severe Acneiform Rash	Cetuximab	Outcome	Cetuximab Dose Modification
1 st Occurrence	Delay infusion 1 to 2 weeks	Improvement No Improvement	Continue at 250 mg/m ² Discontinue Cetuximab
2 nd Occurrence	Delay infusion 1 to 2 weeks	Improvement No Improvement	Continue at 200 mg/m ² Discontinue Cetuximab
3 rd Occurrence	Delay infusion	Improvement	Continue at 150 mg/m ²

Table 4.5.3.2-1: Cetuximab Dose Modification Guidelines for Rash			
Severe Acneiform Rash	Cetuximab	Outcome	Cetuximab Dose Modification
	1 to 2 weeks	No Improvement	Discontinue Cetuximab
4 th Occurrence	Discontinue Cetuximab permanently		

For Cisplatin, Carboplatin and 5-FU:

Recommendations for dose modifications for cisplatin, carboplatin and 5-FU should be considered with local institutional standards. The dose levels for 5-FU, cisplatin and carboplatin are listed in Table 4.5.3.2-2:

Table 4.5.3.2-2: Dose Levels for 5-FU, Cisplatin, and Carboplatin

	5-FU Dose	Cisplatin Dose	Carboplatin Dose

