4.5.3.2.1 Recommended Dose Modifications for Hematologic Toxicity

Dose adjustments are based on nadir blood counts since the preceding chemotherapy administration. Dose level adjustments are relative to that of the preceding administration, and are described in Table 4.5.3.2-3

Table 4.5.3.2-3: 5-FU, Cisplatin, and Carboplatin Dose Modifications for Hematologic Toxicity^a

Drug Related Toxicity	5-FU	Cisplatin	Carboplatin
Neutrophils (ANC) < 500/mm ³ lasting ≥ 5 days	Decrease by -1 dose level	Decrease by -1 dose level	Decrease by -1 dose level
Febrile neutropenia (body temperature ≥ 38.5°C and ANC < 1,000/mm ³)	Decrease by -1 dose level	Decrease by -1 dose level	Decrease by -1 dose level
Platelets < 25,000/mm ³	Decrease by -1 dose level	Decrease by -1 dose level	Decrease by -1 dose level
Platelets < 50,000/mm ³ with significant bleeding or requiring blood transfusion	Decrease by -1 dose level	Decrease by -1 dose level	Decrease by -1 dose level
Grade 4 hemoglobin (< 6.5 g/100 mL)	Decrease by -1 dose level	Decrease by -1 dose level	Decrease by -1 dose level

^a If considered in the best interest of the participant, and consistent with local practice, investigators may decide to use supportive measures/treatment, and/or secondary prophylaxis instead of dose reductions for the next cycle.

Also, if toxicity can clearly be attributed to one of the drugs, the investigator may choose to only dose reduce one of the cytotoxics

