4.5.3.2.2 Recommended Dose Modifications for Non-hematologic Toxicity

Dose adjustments for non-hematologic toxicity during treatment are described in Table 4.5.3.2-4. All dose modifications should be made based on the worst grade toxicity per CTCAE v4.0.

Table 4.5.3.2-4: 5-FU, Cisplatin, and Carboplatin Dose Modifications for Non-hematologic Toxicity^a

Drug Related Toxicity	5-FU	Cisplatin	Carboplatin
Nausea/vomiting ≥ Grade 3 despite optimal medical treatment	Decrease by -1 dose level	Decrease by -1 dose level	Decrease by -1 dose level
Stomatitis ≥ Grade 3	Decrease by -1 dose level	Decrease by -1 dose level	Decrease by -1 dose level
Diarrhea ≥ Grade 3 despite optimal medical treatment	Decrease by -1 dose level	Decrease by -1 dose level	Decrease by -1 dose level
Neuropathy (sensory or motor), Grade 2 lasting > 7 days OR Grade 3 lasting < 7 days	No modification	Decrease to -2 dose level	No modification
Neuropathy Grade 4 (sensory or motor)	No modification	Discontinue	No modification
Nephrotoxicity (Creatinine Clearance 50-59mL/min or Grade 3 Creatinine)	No modification	Decrease to -2 dose level or according to local practice	No modification
Total bilirubin > 1.5 x ULN	50% of previous dose	No modification	No modification
Total bilirubin > 2.5 x ULN	25% of previous dose	No modification	No modification
Total bilirubin > 4.0 x ULN	Discontinue	No modification	No modification
Other Grade ≥ 3 toxicities (except fatigue and transient arthralgia and myalgia)	Decrease by -1 dose level	Decrease by -1 dose level	Decrease by -1 dose level

^a If considered in the best interest of the participant, and consistent with local practice, investigators may decide to use supportive measures/treatment, and/or secondary prophylaxis instead of dose reductions for the next cycle. Also, if toxicity can clearly be attributed to one of the drugs, the investigator may choose to only dose reduce one of the cytotoxics.

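### Arm B dose tables reduce or continue a drug for some Grade 4 and prolonged Grade 3 toxicities that Section 4.5.5.3 lists for permanent discontinuation, and no text says which prevails

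*Protocol*

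**What the plan says.** **Stopping rule.** Protocol Section 4.5.5.3 lists the reasons for permanent discontinuation in Arm B. For Grade 4 it reads "Any drug-related Grade 4 toxicity including laboratory abnormalities the subject will be discontinued from the relevant study drug, with the following exceptions". The exceptions are "Isolated Grade 4 electrolyte abnormalities not associated with clinical sequelae and are adequately managed and corrected within 72 hours of onset" and "Grade 4 neutropenia or lymphopenia ≤ 7 days". A second rule covers "Any Grade 3 non-skin, drug-related adverse event lasting > 7 days, with the following exceptions"; most Grade 3 laboratory abnormalities are exempt from it. The section closes by allowing the other Arm B drugs to continue, at the investigator's discretion, when one is stopped.

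**Dose tables in Section 4.5.3.2.**
- Table 4.5.3.2-3 (hematologic) has a row for "Grade 4 hemoglobin (< 6.5 g/100 mL"). The action is one dose level lower for 5-FU, cisplatin and carboplatin.
- Table 4.5.3.2-1 (cetuximab) "contains the recommended dose modifications for severe (CTCAE v4 Grade 3 or 4) acneiform rash". After improvement, cetuximab continues at 250, 200 and 150 mg/m² for the first, second and third occurrence. It stops if there is no improvement, or at the fourth occurrence.
- Table 4.5.3.2-4 (non-hematologic) lowers all three cytotoxics by one level for nausea/vomiting, stomatitis and diarrhea of Grade 3 or higher, and for "Other Grade ≥ 3 toxicities (except fatigue and transient arthralgia and myalgia").

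**How the sections relate.** Section 4.5 bases treatment modifications on Sections 4.5.2 to 4.5.5 without ranking them, and Section 4.5.1.2 also lists them side by side. Section 4.5.2 says EXTREME dose modifications are to be considered with local institutional standards. Section 4.5.4.3 refers to the Section 4.5.5.3 discontinuation limits for combined AST/ALT and bilirubin values, and to that section's exceptions for delays beyond 6 weeks, but not for the toxicities discussed here.

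**The concern.** A site facing one of these events can find one page that says to stop the drug for good and another that says to reduce it or, for rash, to carry on. Both instructions are in the current protocol and neither refers to the other. The first thing at stake is participant safety: whether a control-arm participant is re-exposed to a drug after a Grade 4 or prolonged Grade 3 toxicity would depend on which section the site consulted.

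The second is how comparator treatment is described. The SAP summarizes relative dose intensity (Section 7.4.1), chemotherapy-arm dose reductions by level (7.4.2.4), adverse events leading to discontinuation (7.6.3) and adverse events leading to dose delay or reduction (7.6.4). The same clinical event would be counted in different tables according to the rule followed.

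**Working it through.** No sample size, power, alpha or event count is involved, so the check is a row-by-row comparison of the three tables with Section 4.5.5.3. A row is called a direct contradiction when the protocol's own wording places a Grade 4 event in it and neither Grade 4 exception applies. It is called an overlap when only part of an open-ended row meets a stopping rule.

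| Table entry | Table action | Section 4.5.5.3 | Result |
|---|---|---|---|
| Grade 4 hemoglobin (4.5.3.2-3) | 5-FU, cisplatin, carboplatin down one level | Grade 4, laboratory values included; hemoglobin not excepted: relevant drug stops | Direct contradiction for the attributed drug |
| Acneiform rash, Grade 4 (4.5.3.2-1) | Cetuximab continues after improvement, occurrences 1 to 3 | Grade 4; rash not excepted: relevant drug stops | Direct contradiction where cetuximab is the attributed drug |
| Acneiform rash, Grade 3 (4.5.3.2-1) | As above | Prolonged Grade 3 rule excludes skin events | No conflict |
| Nausea/vomiting, stomatitis, diarrhea, Grade 3 or higher (4.5.3.2-4) | Three cytotoxics down one level | Stop at Grade 4, or at Grade 3 beyond 7 days | Overlap |
| Other, Grade 3 or higher (4.5.3.2-4) | Three cytotoxics down one level | Stop at Grade 4 unless excepted, or at non-skin Grade 3 beyond 7 days; most Grade 3 laboratory events exempt | Overlap, narrower than the row |

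**Count.** Two direct contradictions plus four overlapping rows (nausea/vomiting, stomatitis, diarrhea, other) gives 2 + 4 = 6 entries.

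**Example of an overlap.** Take drug-related Grade 3 stomatitis lasting 10 days in a participant on starting doses. Under Table 4.5.3.2-4, with the levels in Table 4.5.3.2-2, 5-FU goes from 1000 to 750 mg/m² and cisplatin from 100 to 75 mg/m². Stomatitis is neither a skin nor a laboratory event and 10 > 7 days, so Section 4.5.5.3 lists the same event for permanent discontinuation.

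**Rows not counted.** The neutrophil and platelet rows of Table 4.5.3.2-3 are written as cell counts. Section 4.5.5.3 speaks in grades, for example "Grade 3 drug-related thrombocytopenia associated with bleeding", and the documents do not print the CTCAE limits that link the two. Those rows may raise the same question, but the point does not rest on them.

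**The case against.** The best defense is that the sections are meant to be read together: the discontinuation criteria remove some events and the tables deal with the rest. The tables are labelled as recommended and sit under a sentence on local standards. Footnotes to Tables 4.5.3.2-3 and 4.5.3.2-4 allow supportive measures instead of reduction, or reduction of only one cytotoxic. On this reading the four open-ended rows are loose drafting rather than opposite orders, which is why they are classed here as overlaps. The defense does not rescue the two direct contradictions. A row written for Grade 4 hemoglobin, and a rash table whose stated scope includes Grade 4, have nothing left to deal with for the attributed drug once Grade 4 events are removed. Recommended status gives latitude; it does not tell a site that discontinuation overrides a listed reduction.

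Four stronger readings are tempting but go beyond the text:
- *The hemoglobin row can never apply.* The Grade 4 rule removes only the relevant drug, and the other drugs may continue, so the row can still apply to a cytotoxic not held responsible.
- *The neuropathy rows show the intended pattern.* At Grade 4 they discontinue cisplatin but leave carboplatin and 5-FU unmodified, so they are not a clean model and do not show that Section 4.5.5.3 was meant to prevail.
- *Sites would dose through the toxicity.* For drug-related non-skin, non-laboratory events of Grade 2 or higher, Section 4.5.2.2 delays dosing apart from alopecia and fatigue, and Section 4.5.4.3 generally requires resolution or return to baseline first. The conflict is about what happens after recovery.
- *The efficacy comparison is compromised.* OS is analyzed as randomized, safety is an exploratory objective, and no between-arm test of discontinuation rates is specified. Nothing in the documents shows an effect on the OS analysis.

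**Conclusion.** The point holds in a limited form. Six table entries are affected: two contradict Section 4.5.5.3 outright for the drug to which the event is attributed, and four overlap with it because they have no upper limit on grade or duration. The two contradictions rest only on grades that the protocol states itself. The four overlaps depend on reading each row as written, without an implied ceiling; the Grade 3 part excludes skin events and most laboratory abnormalities.

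How many participants would meet one of these events, and how many sites would follow each section, cannot be derived from the documents. The issue is one of participant safety and consistent conduct in the control arm. It merits correction because permanent stopping is at issue and the remedy is small. Which rule is clinically right is for the sponsor to decide; no position is taken here.

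**What to change.** The sponsor should reconcile Tables 4.5.3.2-1, 4.5.3.2-3 and 4.5.3.2-4 with Section 4.5.5.3 so that each event, at each grade and duration, leads to one action for a given drug. The text should also say which section prevails if an overlap remains. Either the tables or Section 4.5.5.3 could be changed. The cell-count rows can be checked against the applicable grade limits at the same time.

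The cost is protocol wording, by amendment or administrative letter, and a notice to sites. No new data, procedures or analyses are needed.

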4.5.6 Treatment Beyond Disease Progression (Arm A only)

Accumulating evidence indicates a minority of participants treated with immunotherapy may derive clinical benefit despite initial evidence of PD.

Participants will be permitted to continue on nivolumab combined with ipilimumab for treatment beyond initial RECIST 1.1 defined PD up to a total of 24 months total treatment duration from the start of study treatment as long as they meet the following criteria:

- Investigator-assessed clinical benefit and no rapid disease progression
- Participant is tolerating study treatment
- Stable performance status
- Treatment beyond progression will not delay an imminent intervention to prevent serious complications of disease progression (eg, CNS metastases)
- **Participant** provides written informed consent prior to receiving additional nivolumab and ipilimumab treatment, using an ICF describing any reasonably foreseeable risks or discomforts, or other alternative treatment options.

The decision to continue treatment beyond initial investigator-assessed progression should be discussed with the BMS Medical Monitor and documented in the study records. A follow-up scan should be performed within six (6) weeks \pm 1 week of original PD to determine whether there has been a decrease in the tumor size, or continued progression of disease. Subsequent scans should be performed every six (6) weeks \pm 1 week until further progression is determined. In the event of unscheduled scans, efforts should be made to get subsequent scan back on the every six (6) weeks \pm 1 week until further progression is determined.

If the investigator feels that the participant continues to achieve clinical benefit by continuing treatment, the participant should remain on the trial and continue to receive monitoring according to the Time and Events Schedule in [Table 5.1-2](#).

For the participants who continue study therapy beyond progression, further progression is defined as an additional 10% increase in tumor burden from time of initial PD. This includes an increase in the sum of diameters of all target lesions and/ or the diameters of new measurable lesions compared to the time of initial PD. Nivolumab and ipilimumab treatment should be discontinued permanently upon documentation of further progression.

New lesions are considered measureable at the time of initial progression if the longest diameter is at least 10 mm (except for pathological lymph nodes which must have a short axis of at least 15 mm). Any new lesion considered non-measurable at the time of initial progression may become measureable and therefore included in the tumor burden if the longest diameter increases to at least 10 mm (except for pathological lymph nodes which must have a short axis of at least 15 mm). In situations where the relative increase in total tumor burden by 10% is solely due to inclusion of new lesions which become measurable, these new lesions must demonstrate an absolute increase of at least 5 mm.

4.5.7 Management Algorithms for Immuno-Oncology Agents

Immuno-oncology (I-O) agents are associated with AEs that can differ in severity and duration than AEs caused by other therapeutic classes. Nivolumab and ipilimumab are considered immuno-oncology agents in this protocol. Early recognition and management of AEs associated with immuno-oncology agents may mitigate severe toxicity. Management Algorithms have been developed to assist investigators in assessing and managing the following groups of AEs:

- Gastrointestinal

- Renal
- Pulmonary
- Hepatic
- Endocrinopathy
- Skin
- Neurological

The above algorithms are found in both the nivolumab and ipilimumab Investigator Brochures, as well as in [Appendix 2](#).

4.5.8 Treatment of Infusion Reactions

4.5.8.1 Nivolumab or Ipilimumab Infusion Reactions

Since nivolumab and ipilimumab contain only human immunoglobulin protein sequences, they are unlikely to be immunogenic and induce infusion or hypersensitivity reactions. However, if such a reaction were to occur, it might manifest with fever, chills, rigors, headache, rash, pruritus, arthralgias, hypo- or hypertension, bronchospasm, or other symptoms. All Grade 3 or 4 infusion reactions should be reported within 24 hours to the BMS Medical Monitor and reported as an SAE if criteria are met. Infusion reactions should be graded according to NCI CTCAE (Version 4.0) guidelines.

Treatment recommendations are provided below and may be modified based on local treatment standards and guidelines, as appropriate:

For Grade 1 symptoms: (mild reaction; infusion interruption not indicated; intervention not indicated)

- Remain at bedside and monitor participant until recovery from symptoms. The following prophylactic premedications are recommended for future infusions: diphenhydramine 50 mg (or equivalent) and/or acetaminophen/paracetamol 325 to 1000 mg at least 30 minutes before additional nivolumab or ipilimumab administrations.

For Grade 2 symptoms: (moderate reaction requires therapy or infusion interruption but responds promptly to symptomatic treatment [eg, antihistamines, non-steroidal anti-inflammatory drugs, narcotics, corticosteroids, bronchodilators, IV fluids]; prophylactic medications indicated for ≤ 24 hours)

- Stop the nivolumab or ipilimumab infusion, begin an IV infusion of normal saline, and treat the participant with diphenhydramine 50 mg IV (or equivalent) and/or acetaminophen/paracetamol 325 to 1000 mg; remain at bedside and monitor participant until resolution of symptoms. Corticosteroid and/or bronchodilator therapy may also be administered as appropriate. If the infusion is interrupted, then restart the infusion at 50% of the original infusion rate when symptoms resolve; if no further complications ensue after 30 minutes, the rate may be increased to 100% of the original infusion rate. Monitor participant closely. If symptoms recur, then no further nivolumab or ipilimumab will be administered at

that visit. Administer diphenhydramine 50 mg IV, and remain at bedside and monitor the participant until resolution of symptoms. The amount of study drug infused must be recorded on the electronic case report form (eCRF).

- For future infusions, the following prophylactic premedications are recommended: diphenhydramine 50 mg (or equivalent) and/or acetaminophen/paracetamol 325 to 1000 mg should be administered at least 30 minutes before nivolumab or ipilimumab infusions. If necessary, corticosteroids (up to 25 mg of SoluCortef or equivalent) may be used.

For Grade 3 or 4 symptoms: (severe reaction, Grade 3: prolonged [ie, not rapidly responsive to symptomatic medication and/or brief interruption of infusion]; recurrence of symptoms following initial improvement; hospitalization indicated for other clinical sequelae [eg, renal impairment, pulmonary infiltrates]. Grade 4: Life threatening; pressor or ventilatory support indicated)

- Immediately discontinue infusion of nivolumab or ipilimumab. Begin an IV infusion of normal saline and treat the participant as follows: Recommend bronchodilators, epinephrine 0.2 to 1 mg of a 1:1000 solution for subcutaneous administration or 0.1 to 0.25 mg of a 1:10,000 solution injected slowly for IV administration, and/or diphenhydramine 50 mg IV with methylprednisolone 100 mg IV (or equivalent), as needed. Participant should be monitored until the investigator is comfortable that the symptoms will not recur. Nivolumab or ipilimumab will be permanently discontinued. Investigators should follow their institutional guidelines for the treatment of anaphylaxis. Remain at bedside and monitor participant until recovery of the symptoms.

In case of late-occurring hypersensitivity symptoms (eg, appearance of a localized or generalized pruritus within 1 week after treatment), symptomatic treatment may be given (eg, oral antihistamine or corticosteroids).

